AB	May 2, 2017	90702637 Rev/Ver AH	Section 9.3	Add Exclusion Criteria: The investigator believes the subject is not suitable for the study	To be consistent with Section2
AB	May 2, 2017	90702637 Rev/Ver AH	Section 10.3	Add "Enrollment Control"	To be in compliance with China Medical Device GCP
AB	May 2, 2017	90702637 Rev/Ver AH	Section11 Table 11.1	Remove 'Hepatitis B and C biomarker tests' from the blood test and list as only the baseline test	Remove unnecessary tests at follow-ups
AB	May 2, 2017	90702637 Rev/Ver AH	Section 11.5	Add "Post Initial Treatment"	To ensure accuracy
AB	May 2, 2017	90702637 Rev/Ver AH	Section 11.6 Section 11.7 Section 118 Section 11.9	Remove 'Hepatitis B and C biomarker tests' from follow-up test list	Remove unnecessary tests at follow-ups
AB	May 2, 2017	90702637 Rev/Ver AH	Section 11.6 Section 11.7 Section 11.8 Section 11.9	Change to 'Plain scan plus enhanced MRI'	To ensure adequacy of imaging test for HCC
AB	May 2, 2017	90702637 Rev/Ver AH	Section 11.4	Change to'Scanning sequence include coronal T2WI, transect T2WI, T1WI, DWI, enhanced scan using 3D T1WI'	To ensure adequacy of imaging test for HCC
AB	May 2, 2017	90702637 Rev/Ver AH	Section 11.4	Add 'CT scan to monitor the migration of microspheres in case of non-target embolization during treatment'	To ensure adequacy of imaging test for HCC
AB	May 2, 2017	90702637 Rev/Ver AH	Section 12.3.2	Delete "Interim Analysis"	Remove irrelevant content

Revision History

Revision Number	Release Date	Template number and version	Section	Change	Reason for Change
AB	May 2, 2017	90702637 Rev/Ver AH	Section 19.1	Add Table 19.1-1'Incidence rates of expected embolization related adverse events'	To ensure accuracy
AB	May 2, 2017	90702637 Rev/Ver AH	Section 19.4	Add "Benefit-Risk Ratio"	To be in compliance with China Medical Device GCP
AB	May 2, 2017	90702637 Rev/Ver AH	Section 20.3 Table 20.3-1	Change 'First aware of the event in one working day' to 'First aware of the event in 24 hours'	To be in compliance with China Medical Device GCP
AB	May 2, 2017	90702637 Rev/Ver AH	Section 20.5	Delete 'CEC related description'	Remove irrelevant content
AB	May 2, 2017	90702637 Rev/Ver AH	Section 12.1.1 Section 13.3 Appendix E	Add 'EASL tumor response evaluation criteria'	To ensure adequate endpoint assessment
AB	May 2, 2017	90702637 Rev/Ver AH	All Chapters	Add Acronyms when it's first mentioned in the protocol	To ensure accuracy
AC	June 3, 2017	90702637 Rev/Ver AH	Section2 Section9	Change the tumor size in the inclusion criteria to 'diameter <7am for single lesion or maximum 3 lesions with total diameter less than 10cm'; Change BCLC stage from 'A/B' to 'A/B7' on inclusion criteria; Change bilirubin level from '>3mg/dl' to '>2mg/dl' on exclusion criteria	To enroll more appropriate patients
AC	June 3, 2017	90702637 Rev/Ver AH	Section 11	List detailed tests at baseline and follow-ups	To ensure accuracy
AC	June 3, 2017	90702637 Rev/Ver AH	Section 11.4 Section 11.5	Add details on imaging assessment and post-treatment evaluation	To clarify
AC	June 3, 2017	90702637 Rev/Ver AH	All Chapter	Wording	To ensure accuracy
AD	March 23, 2018	90702637 Rev/Ver AH	Contact information	Update contact person	Update project manager
AD	March 23, 2018	90702637 Rev/Ver AH	Section 8	Add "Study Flow Chart"	To clarify study flow
AD	March 23, 2018	90702637 Rev/Ver AH	Section 9.2	Add "individual diameter<7cm, maximum 3 lesions with >1cm in diameter" for multiple tumors	To clarify
AD	March 23, 2018	90702637 Rev/Ver AH	Section 9.2 & Attachment A	Change the version of HCC management guideline from 2011 to 2017	To be consistent with up to date HCC management guideline

Form/Template 90702637 Rev/Ver AH STOPPER China Protocol, 92040370 Rev/Ver AD Page 5 of 59

Revision History

Revision Number	Release Date	Template number and version	Section	Change	Reason for Change
AD	March 23, 2018	90702637 Rev/Ver AH	Section 9.3	Change "Portal vein invasion" to "Invasion of the main or primary branches of the portal vein"	To clarify
AD	March 23, 2018	90702637 Rev/Ver AH	Section 9.3	Remove #3 "3. Prior intra- arterial embolization or chemotherapy or systemic therapy for treatment of HCC"	Redundant with #6 of the inclusion criteria
AD	March 23, 2018	90702637 Rev/Ver AH	Section 11.3	Change to "Before any study specific tests or procedures are performed" to "Before the screening procedure"	To ensure the accuracy of the description of study procedure
AD	March 23, 2018	90702637 Rev/Ver AH	Section 11.5	Delete "For subjects with bilobar involvement, each of the two lobes should be treated subsequently with the lobe with the higher tumor burden treated first"	The treatment strategy will be determined by the investigator, which is more consistent with actual clinical practice
AD	March 23, 2018	90702637 Rev/Ver AH	Section 11.10	Delete "Pass the follow-up window (14 days passed the scheduled follow-up time"	To ensure a more reasonable definition of study ending
AD	March 23, 2018	90702637 Rev/Ver AH	Attachment C	Add the measurement unit commonly used in China for serum total bilirubin and serum albumin	To facilitate Child- Pugh score
AD	March 23, 2018	90702637 Rev/Ver AH	All chapters	Wording	To ensure accuracy

2. Protocol Synopsis

A Single-arm Trial of Transcatheter Arterial Chemoembolization with Tandem Microspheres in the Treatment of Localized Hepatocellular Carcinoma					
Study Objective	effic Tan	The primary objective of this study is to evaluate the safety and efficacy of transcatheter arterial chemoembolization with Tandem Microspheres loaded with Epirubicin in the treatment of subjects with localized hepatocellular carcinoma (HCC)			
Study Device	bioc	Tandem Microspheres are spherical, tightly calibrated, biocompatible, non-resorbable, hydrogel microspheres coated with Polyzene®-F, an inorganic polymer.			
Planned Indication(s) for Use		dem Microspheres are indicate riovenous malformations and h			
Device Specifications	Tandem Microspheres are stored in 2 ml and 3 ml sized. They are available in a range of sizes (40, 75, and 100 μ Microspheres used will be at the discretion of the treating physician(s) based on the tumor size and/or vascular structure.				
		Microspheres Diameter	Size (ml)		
		40	2		
		40	3		
		75	2		
		75	3		
		100	2		
		100	3		
Study Design	the s cher Epir hepa in th	s is a prospective, single-arm, resafety and efficacy of transcath moembolization with Tandem I subicin in the treatment of subject atocellular carcinoma. All qual the study and receive transcather ment with Tandem Microsphe	Microspheres loaded with ects with localized ified subjects will be enrolled ter arterial chemoembolization		
Sample Size	109	109 subjects (including 10% loss to follow-up)			
Number of Study Sites	10 c	10 clinical centers will be participating in the study			
Primary Effectiveness Endpoint		The primary effectiveness endpoint for this clinical trial is 6-month objective tumor response rate (ORR).			

Form/Template 90702637 Rev/Ver AH STOPPER China Protocol, 92040370 Rev/Ver AD Page 7 of 59

Secondary Endpoints	ORR at 30-day and 3-month
	• Time to Progression (TTP)
	Time to Extrahepatic Spread
	 Proportion Progression-Free (PPF) at one year
	Overall survival at one year
	The frequency of Tandem treatment associated adverse avents.
	events
Study Enrollment	Subject will be qualified to be enrolled in the clinical trial once signed the IRB/EC approved informed consent, meet all inclusion criteria and does not meet any of the exclusion criteria. All enrolled subjects will receive the transcatheter arterial chemoembolization with Tandem Microspheres. Enrollment timepoint will be based on subject receiving transcatheter arterial chemoembolization treatment with Tandem Microspheres loaded with Epirubicin
Follow-up Plan	Follow-up will be conducted at 30 days and 3, 6, and 12 months post initial treatment. The tests during the follow-ups include:
	 Laboratory (include Complete Blood Count, blood biochemistry, blood coagulation function, renal and liver function, electrolyte, AFP) and imaging tests (include plain scan plus enhanced MRI, Chest plain scan CT) at 30 days and 3, 6 and 12 months post procedure ECG at 3 months post procedure
Study Duration	The study will end when all subjects completed the 12-month follow-up post initial treatment, or withdraw (death, loss to follow-up or withdraw consent).

Form/Template 90702637 Rev/Ver AH STOPPER China Protocol, 92040370 Rev/Ver AD Page 8 of 59

_	
Inclusion Criteria	Subjects may be included in the study only if they meet all of the following criteria:
	1. Subject is able to provide informed consent and must sign the Institutional Review Board/Ethics Committee (IRB/EC) approved Informed Consent Form.
	2. Male or female of age ≥ 18 and ≤ 75 years.
	3. Confirmed diagnosis of HCC according to the diagnostic criteria included in the management guideline issued by China's Ministry of Health in 2017.
	4. HCC is diagnosed for the first time or recurrence of tumor after surgical or ablation treatment.
	5. Single tumor less than 7cm in diameter or multiple tumors with maximum 3 lesions with >1cm in diameter, individual diameter <7cm and less than 10cm in total diameter.
	6. no previous chemotherapy, radiotherapy or transarterial embolization (with or without chemotherapy) for HCC
	7. Preserved liver function (Child-Pugh A or B7).
	8. ECOG Performance Status 0 or 1.

Form/Template 90702637 Rev/Ver AH STOPPER China Protocol, 92040370 Rev/Ver AD Page 9 of 59

Evaluaian Critaria	Cubicata will be analyded for the Callerine		
Exclusion Criteria	 Subjects will be excluded for the following reasons: Presence of vascular invasion or extra-hepatic spread of disease, or diffuse HCC, defined as >50% liver involvement, or arteriovenuous fistula Macrovascular invasion of main or primary branches of portal vein at entry into the study Any contraindication for TACE treatment Any contraindication for Epirubicin administration Advanced liver disease (bilirubin levels >2 mg/dl, AST 		
	or ALT >5 times upper limit of normal) 6. Renal failure or insufficient renal function (Creatinine levels >2 mg/dl)		
	7. Subject unable to receive MRI examination		
	8. Pregnant or breast feeding woman, or plan to become pregnant during treatment or within 12 months of treatment		
	9. couldn't commit reliable birth control measures during treatment or within 12 months of treatment		
	10. Subject is participating other investigational drug or device clinical trial within 30 days of signing the informed consent		
	11. Subject is not suitable to participate in the study as judged by investigator		
Statistical Methods			
Primary Study Hypotheses	The primary hypothesis is that the 6-month ORR in the Tandem microspheres embolization and drug delivery arm is higher than the performance goal (PG).		
	The null (H_0) and alternative (H_1) hypotheses for this primary endpoint are presented below.		
	$H_0: P_e \leqslant PG$		
	$H_1: P_e > PG$		
	where P _e is the expected 6-month ORR (%).		
Statistical Test	A normal approximation test will be used to assess the one-sided hypotheses of the test device superior to the PG		

Form/Template 90702637 Rev/Ver AH STOPPER China Protocol, 92040370 Rev/Ver AD Page 10 of 59

Success Criteria for the PG	The test device will be concluded to be superior to the PG in the primary analysis if the one-sided lower 97.5% confidence bound for the test device performance in 6-month ORR is greater than PG.
Sample Size Parameters	The overall sample size (N=109) is driven by the primary effectiveness endpoint. • Power ≥ 85% • One-sided significance level = 2.5% (alpha) • PG for 6-month ORR = 45% • Expected 6-month ORR = 60% • Total N=98 subjects are required for 6-month assessment • Attrition rate = 10% (loss to follow-up in 6 months) • Approximately N=109 subjects to enroll

Form/Template 90702637 Rev/Ver AH STOPPER China Protocol, 92040370 Rev/Ver AD Page 11 of 59

3. Table of Contents

1.	Title Page	1
2.	PROTOCOL SYNOPSIS	6
3.	TABLE OF CONTENTS	11
4.	Introduction	16
5.	DEVICE DESCRIPTION	17

27	ABBREVIATIONS AND DEFINITIONS	52

Form/Template 90702637 Rev/Ver AH STOPPER China Protocol, 92040370 Rev/Ver AD Page 15 of 59

3. Table of Tables

Table 11.1: Baseline and Follow-up Evaluation Plan	24
Table 19.1-1: Potential Complications and Incidence Rates	
Table 20.2-1: Safety Reporting Definitions	
Table 20.3-1: Criteria for Assessing Relationship of Study Device or Procedure to Advers	
Table 20.4-1: Investigator Reporting Requirements	
Table 27.1: Terms and Abbreviations	53
Table 27.2: Definitions	54

Form/Template 90702637 Rev/Ver AH STOPPER China Protocol, 92040370 Rev/Ver AD Page 16 of 59

4. Introduction

Hepatocellular carcinoma (HCC) is the most common primary malignancy of the liver. It is one of the most common cancer in the world, the third most common cause of cancer-related death¹. A majority of HCC cases (60% to 80%) arise due to chronic hepatitis and cirrhosis. Major etiologies of liver cirrhosis include chronic hepatitis B and C, alcohol consumption, steatosis, diabetes, certain medications or exposures to toxic agents and genetic and metabolic diseases². Obesity has also been identified as an independent risk factor for developing HCC^{3,4}.

HBV is the most frequently underlying cause of HCC in Asia. HBV carriers have a 5 to 15-fold increased risk of HCC compared to the general population. Chronic HBV carriers in Asia develop HCC at an annual rate of 0.4-0.6%. In Western countries and Japan, the main risk factor is HCV infection and excessive alcohol intake, along with other causes of cirrhosis. The annual incidence rate of HCC in subjects with hepatitis C is 3.7-7.1%⁵.

Various staging and classification systems have been proposed for HCC, which help to select treatment strategies, assess prognosis, and compare results from different clinical studies⁶. The Barcelona Clinic Liver Cancer (BCLC) staging system has been used for stratification of subjects with HCC in the practice guidelines established by the American Association of the Study of Liver Diseases (AASLD)^{7,8}. In addition to estimating prognosis, the BCLC staging system also links staging to treatment recommendations. In this staging system, intermediate stage (BCLC-B) is formed by those subjects who are asymptomatic and harbor multifocal HCC without vascular invasion or extrahepatic spread and have preserved liver function (Child-Pugh Class A or B) and normal performance status (Eastern Cooperative Oncology Group Performance Status ECOG PS) of 0. Chemoembolization is recommended as the main treatment strategy for subjects in this intermediate stage.

Transarterial chemoembolization (TACE) is a commonly used procedure to treat liver cancers using a catheter to deliver both chemotherapy medication and embolization materials into the blood vessels that lead to the tumor. The American Cancer Society, Society of Interventional Radiology and the National Comprehensive Cancer Network have identified TACE procedures where doxorubicin (alone or mixed with other cytotoxic agents such as cisplatin and/or mitomycin C), is mixed with ethiodol and injected intra-arterially as an oily mixture into the vasculature of the tumor as the standard of care for subjects with unresectable hepatocellular carcinoma (HCC)⁷.1 Following the TACE procedure, embolic particles are injected to slow the blood flow to the tumor's vasculature. This procedure is also known as conventional TACE (cTACE). Although cTACE has shown survival benefit in properly selected HCC patients from two randomized studies and a meta-analysis, ⁹⁻¹¹ this often is associated with marked symptoms of postembolization syndrome and is not well tolerated by patients with advanced disease. ¹²⁻¹⁴

Unlike cTACE, chemoembolization with drug-eluting beads (DEB-TACE) using doxorubicin has been found to be well tolerated with minimal postembolization syndrome

symptoms. A recent randomized study comparing cTACE and DEB-TACE has shown better tolerability and fewer complications associated with DEB-TACE¹⁵⁻¹⁸.

In order to 1) minimize the loss of doxorubicin into the bloodstream; 2) prolong the residence time of doxorubicin at the tumor site; and 3) standardize TACE procedures, microsphere technology has advanced to load doxorubicin using drug eluting beads (DEB) before injection. The drug eluting bead procedure (DEB-TACE) is designed to embolize the HCC vasculature and release drug in a controlled manner. Multiple clinical trials in Europe and in the US using DEB-TACE to treat HCC have demonstrated safety, and varying degrees of success of efficacy.

5. Device Description

5.1. Device Description

Tandem Microspheres are 510(k) FDA cleared for embolization of arteriovenous malformations (AVM) and hypervascular tumors (HVT) including hepatoma. Tandem Microspheres are spherical, tightly calibrated, biocompatible, non-resorbable, hydrogel microspheres coated with an inorganic perfluorinated polymer (Polyzene®-F). They are available in a range of sizes suitable for embolic therapy. Tandem Microspheres are opaque in color.

Tandem Microspheres offer:

• Deep penetration into the tumor vasculature due to very small sized 40, 75, and 100 µm Microspheres.

Microspheres Diameter	Size (ml)
(µ])	
40	2
40	3
75	2
75	3
100	2
100	3

- High confidence when performing superselective and targeted embolization procedures as 95% of the microspheres are within the stated size variance.
- Controlled embolization with precisely formulated and standardized microspheres.
- Transcatheter arterial chemoembolization treatment with Tandem Microspheres loaded with epirubicin.

5.2. Device Labeling

STOPPER China Manuel of Operations includes Instruction for Use for Tandem

Form/Template 90702637 Rev/Ver AH STOPPER China Protocol, 92040370 Rev/Ver AD Page 18 of 59

Microspheres. The labeling includes the following information:

- Product Name
- UPN
- Lot Number
- Specification (Diameters of microspheres in µm) and dosage (ml)
- Expiration Date

The labeling of products used for STOPPER China clinical trial should include the following statement:

Used for clinical trial only

The device labeling in Chinese weill be provided per China's regulatory requirement.

6. Study Objective

The primary objective of the study is to evaluate the safety and efficacy of transcatheter arterial chemoembolization with Tandem Microspheres loaded with Epirubicin in the treatment of subjects with localized hepatocellular carcinoma (HCC).

[figure not shown]
7. Study Endpoints

The primary efficacy endpoint is overall ORR at 6 months. The secondary endpoints are:

- ORR at 30 days and 3-month
- Time to Progression (TTP)
- Time to Extrahepatic Spread
- Proportion Progression-Free (PPF) at one year
- Overall survival at one year
- The frequency of treatment associated adverse events

8. Study Design

This is a prospective, single-arm, multicenter study. The flow chart of the study is as follows:

Form/Template 90702637 Rev/Ver AH STOPPER China Protocol, 92040370 Rev/Ver AD Page 20 of 59

8.1. Study Plan

The study will enroll 109 subjects with confirmed diagnosis of localized HCC based on the 2017 Guideline at 10 study sites. Each subject will be followed for 12 months after transcatheter arterial chemoembolization with Tandem Microspheres loaded with Epirubicin(subjects will be followed at 30-day, 3-month, 6-month and 12-month). ORR at 6 months will be assessed as the primary endpoint.

8.2. Treatment Plan

The study will consecutively enroll 109 qualified HCC subjects according to the diagnostic criteria included in the management guideline issued by China's Ministry of Health in 2017. All subjects will receive transcatheter arterial chemoembolization with Tandem Microspheres loaded with Epirubicin. Drug-loaded Tandem microspheres will be delivered into the tumor's vasculature by superselective catheter positioning. The size and specification of microspheres used in the treatment will be decided by the physician based on the tumor size and/or vascular structure. The dose of epirubicin and the volume of Tandem will be at the discretion of the physician based on the subjects's tumor situation. The treatment end point should be devascularization of tumor/lesion and delivering sufficient dose of epirubicin. If after delivering the desired drug/embolization dose, blood flow is still detectable in the tumor; then the procedure can either be stopped, or use bland Tandem microspheres to reach stasis based on the subject's condition. Prior to the procedure, the treating physician must carefully read and be familiar with the appropriate product IFU/DFU including the Loading Guidance.

DEB-TACE General Procedural Considerations

- Prior to the procedure, angiography of the hepatic and mesenteric arteries is performed to map the liver vascular anatomy, identify the tumor-feeding arteries and check for arteriovenous shunts.
- The goal is to deliver drug-loaded TANDEM embolic particles into the tumor's vasculature as selectively as possible. Subjects might be treated via segmental or lobar infusion if a selective or superselective approach is not feasible due to the subject's anatomy and pathology.
- Delivery of the microspheres will stop when either the total targeted microspheres have been delivered or a near stasis (slowed contrast flow for 2-5 heartbeats) endpoint has been reached.
- The doxorubicin-loaded TANDEM microspheres should be injected slowly into the tumor feeding vessels. SLOW INJECTION IS ESSENTIAL FOR BEST RESULTS. When flow starts to decrease, stop, wait several minutes, and then reevaluate. Flow generally will increase again and additional volume of the microspheres can be delivered as microvasculature relaxes after initial blockage.

Form/Template 90702637 Rev/Ver AH STOPPER China Protocol, 92040370 Rev/Ver AD Page 21 of 59

- The goal is to saturate as much of the tumor's vascular bed as possible. The procedure is considered a technical success when the desired devascularization is achieved, or the desired dose is injected.
- If small tumor feeder arteries are missed on the first treatment, they can be addressed during a subsequent treatment.
- No embolization material other than Tandem microspheres should be used during the DEB-TACE procedure

DEB-TACE treatment can be performed for a maximum of 4 times until complete tumor response is observed on imaging or one or more of the following events occurs: Imaging assessment not indicates partial response by mRECIST after two treatments within 6 months; Development of main portal vein thrombosis or extrahepatic spread of disease; Progression to ECOG performance status ≥ 2 or evolution to sustained hepatic decompensation; Intolerable to treatment; Occurrence of any serious adverse event that would prompt the discontinuation of treatment. Other treatment can be initiated per investigator's discretion if no partial response is reached after two consecutive treatments. The investigator may choose adequate treatment option if new hepatic lesion or extrahepatic metastasis appears. Any antiangiogenic drug, anti-cancer chemotherapy, immunotherapy, molecular therapy, and any investigational therapy are not allowed during the Tandem microspheres treatment. If necessary, appropriate anti-viral and/or liver protection treatments can be prescribed to chronic hepatitis patients.

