12.1.1.2. Sample Size

The overall sample size is driven by the primary effectiveness endpoint. Approximately 109 subjects are planned to be enrolled in the study. The sample size justification is based on the following assumptions.

- Power $\geq 85\%$
- One-sided significance level = 2.5% (alpha)
- PG for 6-month ORR = 45%
- Expected 6-month ORR = 60%
- A minimum of 98 evaluable subjects are required for 6-month assessment
- Attrition rate = 10% (loss to follow-up in 6 months)
- A sample size of 109 subjects will be enrolled in the study

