3.1.1 Definition of the ORR

Objective tumor response will be assessed by two response evaluation systems for solid tumors:

- European Association for the Study of the Liver (EASL); and
- Modified Response Evaluation Criteria in Solid Tumors (mRECIST).

The EASL and mRECIST responses measure on MRI in HCC subjects treated with chemoembolization to predict long-term survival. The mRECIST response demonstrated higher survival correlation than the EASL (cf. Prajapati et al, 2013 Annuals of Oncology).

EASL Response Assessment of Target Lesion for HCC:

Response Category	EASL Criteria
Complete Response (CR)	Disappearance of all known disease and no new lesions determined by two observations not less than 4 weeks apart
Partial Response (PR)	At least 50% reduction in total tumor load of all measurable lesions determined by two observations not less than 4 weeks apart
Stable Disease (SD)	Any cases that do not qualify for either PR or PD
Disease Progression (PD)	At least 25% increase in size of one or more measurable lesions or the appearance of new lesions

mRECIST Response Assessment of Target Lesion for HCC:

Response Category	mRECIST Criteria
Complete Response (CR)	Disappearance of any intratumoral arterial enhancement in all target lesions
Partial Response (PR)	At least a 30% decrease in the sum of the diameters of viable (enhancement in the arterial phase) target lesions, taking as reference the baseline sum of the diameters of target lesions.
Stable Disease (SD)	Any cases that do not qualify for either PR or PD
Disease Progression (PD)	An increase of at least 20% in the sum of the diameters of viable (enhancing) target lesions, taking as a reference the smallest sum of the diameters of viable (enhancing) target lesions recorded since treatment started.

A responder is for a subject being assessed as CR or PR as opposed to a non-responder is for being assessed as SD or PD (i.e. numerator). Subjects with valid assessment (i.e. CR, PR, SD, or PD) will be considered as evaluable subjects (i.e. denominator).

A subject without 6 month tumor assessment after the treatment initiation (i.e. the 1st DEB-TACE) will be regarded as a missing data and will be excluded from the primary effectiveness endpoint analysis.

3.1.2 Effectiveness Hypotheses

The primary effectiveness hypothesis to be tested is that the 6-month ORR in subjects treated with Tandem meets the PG at a one-sided significance level of 2.5%.

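### Other HCC treatment started before month 6 has no scoring rule, so a response after Tandem has failed can count for Tandem in the primary ORR

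*Protocol*

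**What the plan says.** **Treatment rules.** Protocol 8.2 gives two routes to other HCC treatment. It may begin at the investigator's "discretion if no partial response is reached after two consecutive treatments". For new disease the text is: "The investigator may choose adequate treatment option if new hepatic lesion or extrahepatic metastasis appears". The bar on systemic and investigational cancer therapy in the same section applies only while Tandem treatment is under way.

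**Scoring rules.** SAP 3.1.1 makes CR or PR a response and SD or PD a non-response. It sets the denominator as follows: "Subjects with valid assessment (i.e. CR, PR, SD, or PD) will be considered as evaluable subjects (i.e. denominator"). The only stated exclusion is a subject with no 6-month tumor assessment. Protocol 12.1.1.1 ties the hypothesis test to EASL.

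**Analysis set.** SAP 4.1 uses a per-protocol basis, and Protocol 12.2.1 uses per protocol and as treated. The only membership condition in either is receipt of the first treatment. SAP 5.4, whose title covers drop-outs and deviations, lists retention measures only. Protocol 12.3.3 and SAP 5.5 plan sensitivity analyses for missing outcomes only.

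**The concern.** The first route opens because Tandem has not produced a response. If the subject then receives something else and is in CR or PR at month 6, the scan reflects that other treatment, yet nothing in SAP 3.1.1 stops it from entering the numerator. Because switching follows failure, scoring the later scan mainly turns failures into responders. In a single-arm trial against a fixed 45% goal, every such subject moves the estimate towards success, and this is the trial's only hypothesis test (SAP 2). The existing sensitivity analyses would not reveal it, because a switcher with a scan is not missing.

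**Working it through.** **1. Inputs (Protocol 12.1.1.2).** One-sided alpha 2.5%; power at least 85%; goal 45%; expected ORR 60%; 98 evaluable; 10% attrition; 109 enrolled.

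**2. The plan's own figure.** One-sample normal approximation, with the null variance for alpha and the alternative variance for power:

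n = [(1.960 × √(0.45 × 0.55) + 1.036 × √(0.60 × 0.40)) / 0.15]² = 97.7, so 98. Approximate power at 98 is 85.1%. Enrolment: 98 / 0.90 = 108.9, so 109. The design reproduces.

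**3. Cut-off.** With 54/98 = 55.1%, z = (0.5510 − 0.45) / √(0.45 × 0.55 / 98) = 2.01, one-sided p = 0.022, and the lower bound is 0.4525. This matches the output in SAP 7.2. With 53/98, z = 1.81 and the lower bound is 0.442, so 54 is the smallest passing count. SAP 3.1.5 names 52/98, but that gives z = 1.60, p = 0.054 and a lower bound of 0.432, which does not clear 45%; 54 is used here. At 54/98 the exact false-pass probability at a true 45% is 2.8%, and exact power at 60% is 86.3%.

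**4. Can a switch come before the endpoint scan?** Protocol 11.6 puts the first evaluation at day 30, a second treatment within 14 days of it, and a further evaluation 30 days later: 30 + 14 + 30 = day 74 nominally. The 6-month scan is at day 183 ± 14, and 183 − 74 = 109 days.

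**5. Do the EASL criteria block it?**
- New lesions are PD, and CR requires that there be none. This largely guards the new-disease route. No rule carries an earlier PD forward to month 6, however.
- CR and PR need two observations at least 4 weeks apart. After day 74 the scheduled follow-up scans are day 91 ± 14, day 183 ± 14 and day 365 ± 14. A response that begins after the switch would have to be visible at the 3-month scan (17 days later nominally, 31 days at the end of the window), or else be confirmed at month 12. The plan does not name the confirming visits, so either reading is open.

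The guards reduce the problem and do not remove it. The route through no partial response after two treatments is untouched by the new-lesion rule.

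**6. Effect on the test.** Let s be the net share of all evaluable subjects who are month-6 responders only because of other treatment. The counted ORR is 0.45 + s, and the false-pass probability is P(X ≥ 54), with X binomial(98, 0.45 + s). One point of s is about one subject in 98.

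| s (points) | False-pass probability |
|---|---|
| 0 | 2.8% |
| 1 | 4.4% |
| 2 | 6.6% |
| 3 | 9.6% |
| 5 | 18.2% |

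The documents do not give s; it is an assumed range. As switch rate × response rate after switching: 10% × 10% = 1 point; 20% × 10% = 2 points; 10% × 50% or 20% × 25% = 5 points.

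**7. Dropping switchers is no cure.** If 10% of subjects switch, none of them responds, and all are removed as outside per protocol, n falls from 98 to 88 and the apparent ORR at a true 45% is 0.45 / 0.90 = 50%. The cut-off becomes 49/88 and the exact false-pass probability is 16.9%.

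**8. Power under the fix.** If the planned 60% already means response without other therapy, the sample size stands. If it includes s points from switchers, exact power at 54/98 is 81.3% (s = 1), 75.4% (s = 2) or 53.4% (s = 5). By the formula in step 2, 85% power would need 131 evaluable subjects for 58% against 45%, or 223 for 55% against 45%.

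**The case against.** **The plan is silent; it does not state that other therapy is ignored.** A reader might infer that every such response is automatically credited to Tandem. The documents do not support that: the per-protocol set is undefined and could be read to exclude switchers, and EASL confirmation would stop some late responses. What stands is that crediting is possible under the text. A permitted switch is also not obviously a deviation, and exclusion brings its own upward bias (step 7).

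**The new-disease sentence is a weak basis.** This is correct. EASL makes a new lesion PD, so the main weight rests on the route for no partial response after two treatments.

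**The large error rates are not established.** A reader might take 18% or more as the trial's actual error. That needs, for example, half of switchers to respond when 10% switch. This would exceed the 45% assumed for Tandem itself, in subjects already selected for failure. At 10% switching with a tenth responding, the figure is 4.4%.

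**The goal may be on the same footing.** SAP 3.1.6 takes the goal from a last-observation-carried-forward analysis of a modified intention-to-treat population. How that trial treated other therapy is not given. If it counted responses regardless, the stricter rule would set Tandem a harder comparison than the goal's own definition. Bias relative to that definition therefore cannot be measured here, which is a reason to report both versions.

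**The fix has a price.** Sites decide on further treatment (Protocol 11.5), while the core laboratory supplies the endpoint data (SAP 4.2). A subject whom the core laboratory reads as a responder to Tandem could become a non-responder through a site decision. This stands as a cost of a conservative rule.

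**Conclusion.** The concern holds as a gap in the definition of the primary endpoint. The protocol permits other HCC treatment well before the month-6 scan, and the SAP neither conditions response on it nor says how such subjects are analysed. As an estimate of response to Tandem alone, the ORR can be biased upward. The size is unknown: net gains of 1, 2 or 5 points give false-pass probabilities of 4.4%, 6.6% or 18.2%, against 2.8% with none. These figures assume a true Tandem ORR of 45%, 98 evaluable subjects, the 54/98 cut-off and independent outcomes. Even about two subjects in 98 more than double the error. The documents do not show that the bias is large, that the new-disease route contributes much to it, or that it exceeds whatever is built into the goal.

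**What to change.** 1. Add to SAP 3.1.1: any subject who begins non-study anti-HCC treatment before the 6-month assessment is a non-responder in the primary analysis and remains in the denominator.
2. State in SAP 4.1 that such subjects are not removed under the per-protocol definition.
3. Report the ORR regardless of other treatment as a prespecified sensitivity analysis. This also covers the case where the goal's source trial counted responses that way.
4. Make sure the eCRF holds the type and start date of other HCC treatment, including non-drug treatment. Protocol Table 11.1 has a row for concomitant medication but none for non-drug HCC treatment after baseline.
5. State whether the expected 60% includes responses after other therapy.

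The cost is SAP wording, one table, a small eCRF addition and a possibly lower observed ORR. If the 60% does include such responses, power falls below the stated 85% (about 75% if 2 points are included). The investigator's freedom to treat is unchanged; only the scoring is affected.
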